4.1.1 Primary endpoint

The primary endpoint is treatment success, defined as not requiring any of the following by Day 15:

- Invasive mechanical ventilation or
- Extracorporeal membrane oxygenation (ECMO).

4.1.2 Secondary endpoints supporting the primary objective

- Time to mechanical ventilation.
- Change from baseline in MEWs score.
- Change from baseline in resting SpO₂.
- Change from baseline in PaO₂/FiO₂.

- Change from baseline in hemogasanalysis.
- Change from baseline in oxygen supplementation.
- Amelioration of the findings of high-resolution CT scan or X-ray of the chest.
- Change from baseline in hyperinflammatory parameters during treatment until Day 15 with measurements performed every 3 days:
 - o Ferritin
 - o LDH
 - D-dimers
- Change from baseline in other relevant laboratory parameters during treatment until Day 15 with measurements performed every 3 days:
 - WBC with differential counts
 - o RBC
 - o Hb
 - Platelet count
 - o Fibrinogen
 - Complement C3/C4
 - Prothrombin time
 - Cardiac troponin
 - Liver tests (AST, ALT, total bilirubin levels)
 - o CRP
 - Creatinine
 - Electrolytes (Sodium, Potassium and Calcium)
 - Glucose
 - Overall survival.
- Time to hospital discharge.

4.2 Secondary objective

The secondary objective of this study is to evaluate the safety and tolerability profile, including evaluation of the immunogenicity of emapalumab and anakinra, of intravenous (i.v.) administrations of emapalumab and anakinra in patients with SARS-CoV-2 infection.

4.2.1 Secondary endpoints supporting the secondary objective

Safety endpoints of this study are:

- Treatment-emergent serious adverse events (SAEs).
- Adverse events leading to premature discontinuation of study treatment.
- Infusion related reactions including anaphylactic/anaphylactoid reactions.
- Treatment emergent adverse events of special interest:
 - Emapalumab treatment group: All new infections.
 - Anakinra treatment group: Severe neutropenia.
- Treatment-emergent laboratory abnormalities.

- Presence of anti-drug antibodies (ADAs) and neutralizing antibodies (Nabs) against emapalumab and anakinra.
- •

4.3 Exploratory objective

An exploratory objective of this study is to evaluate the clinical status based on a 7-point ordinal scale.

An exploratory objective of this study is to evaluate the PK of emapalumab and anakinra.

An exploratory objective of this study is to assess the effect of anakinra and emapalumab on CXCL9, IFN γ , IL-1, IL-6, sIL-2R and selected biomarkers relevant for hyperinflammation.

4.3.1 Exploratory endpoints

Clinical status based on a 7-point ordinal scale.

The scale consists of the the following categories:

- 1. Death
- 2. Hospitalized, requiring invasive mechanical ventilation or extracorporeal membrane oxygenation (ECMO)
- 3. Hospitalized, requiring non-invasive ventilation or high flow oxygen devices
- 4. Hospitalized, requiring supplemental oxygen
- 5. Hospitalized, not requiring supplemental oxygen requiring ongoing medical care
- 6. Hospitalized, not requiring supplemental oxygen no longer requires ongoing medical care
- 7. Not hospitalized

PK parameters will be calculated for emapalumab and anakinra by non-compartmental analysis and population analysis, as applicable.

PD biomarkers: Change from baseline in CXCL9, IFN γ , IL-1, IL-6, sIL-2R and selected biomarkers relevant for hyperinflammation.

5 Investigational plan

5.1 Overall study design and plan

[figure not shown]
This is a randomized, open-label, parallel group, 3-arm multicenter study to investigate the efficacy and safety of emapalumab and anakinra in reducing hyper-inflammation and respiratory distress in adult patients with a documented SARS-CoV-2 infection.

The study consists of screening, a 2-week treatment period and an 8-week follow-up period.

The 2-week treatment period is open, and the patients will be randomized to treatment with emapalumab, anakinra or standard of care in a 1:1:1 ratio. Emapalumab will be administered as i.v. infusions every 3rd day for a total of 5 infusions (Days 1, 4, 7, 10, 13). Anakinra will be administered as 4-times daily i.v. infusions for 15 days (Days 1 to 15). The primary endpoint will be evaluated at Day 15.

An early on-site follow-up visit will be performed at Day 28. A follow-up by visit or phone call will be performed 4 and 8 weeks after the end of the treatment period (Weeks 6 and 10).

The study duration for an individual patient will not exceed 10 weeks. The end of the study is defined as last patient last follow-up visit/phone call.

ANA = anakinra EMA = emapalumab SoC = Standard of care

The study design has a total sample size of 54 patients and consists of two stages. At the end of Stage 1, the success rates are compared between each of the two treatment arms and standard of care and there is the potential to stop for futility.

A data review committee composed of independent experts in intensive care, inflammation, infection diseases will be involved in study oversight, safety monitoring and interpretation of the study results.

A safety review committee consisting of internal Sobi members (voting) and coordinating investigators (non-voting) members is established to monitor study participant safety in the study. Clinical safety information will be monitored and reviewed on a continuous basis by the SRC from study start to database lock. Details are described in a separate written operating procedures for the SRC.

In patients showing worsening of clinical condition, independently of the treatment arm, the Investigator is completely free to decide to introduce any drug considered necessary for a given patient as rescue treatment.

5.2 Discussion of study design, including the choice of control groups

5.3 Selection of study population

5.3.1 Inclusion criteria

A patient must fulfill the following criteria in order to be included in the study:

- 1. Signed informed consent provided by the patient, or by the patient's legally authorized representative(s), as applicable.
- 2. Documented presence of SARS-CoV-2 infection as per hospital routine.
- 3. Age > 18 to < 85 years at the time of screening.
- 4. Presence of respiratory distress, defined as:
 - a. $PaO_2/FiO_2 < 300 \text{ mm Hg and } >200 \text{ mm Hg or}$
 - b. RR \geq 30 breaths/min or
 - c. $SpO_2 < 93\%$ in air at rest.

Note: Patients given CPAP ventilator support are eligible for inclusion.

- 5. Presence of hyperinflammation defined as:
 - a. Lymphocyte counts:
 - < 1000 cells/ μ L, in patients who have not received systemic glucocorticoids for at least 2 days prior to the assessment of the lymphocyte count
 - < 1200 cells/ μ L, in patients who have received systemic glucocorticoids for at least 2 days prior to the assessment of the lymphocyte count

and

- b. One of the following three criteria:
 - i. Ferritin > 500ng/mL
 - ii. LDH > 300 U/L
 - iii. D-Dimers > 1000 ng/mL

5.3.2 Exclusion criteria

The presence of any of the following will exclude a patient from inclusion in the study:

1. Patients in mechanical ventilation or with MEWS score >4 with evidence of moderate or above ARDS (Berlin definition) or severe respiratory insufficiency or evidence of rapid worsening (respiratory distress requiring mechanical ventilation or presence of shock or presence of concomitant organ failure requiring ICU admission).

Confidential

Note: For the evaluation of patient eligibility, temperature will not be considered in the calculation of the total MEWS score since presence of fever is a hallmark of SARS-CoV-2 infection.

- 2. Impairment of cardiac function defined as poorly controlled heart diseases, such as NYHA class II (mild) and above, cardiac insufficiency, unstable angina pectoris, myocardial infarction within 1 year before enrollment, supraventricular or ventricular arrhythmia need treatment or intervention.
- 3. Severe renal dysfunction (estimated glomerular filtration rate ≤ 30 mL/min/1.73 m²) or receive continuous renal replacement therapy, hemodialysis, or peritoneal dialysis.
- 4. Uncontrolled hypertension (seated systolic blood pressure >180mmHg, or diastolic blood pressure >110mmHg).
- 5. Administration of plasma from convalescent patients who recovered from SARS-CoV-2 infection.
- 6. Clinical suspicion of active or latent tuberculosis.
- 7. History of hypersensitivity or allergy to any component of the study drug.
- 8. Pregnant women.
- 9. Existence of any life-threatening co-morbidity or any other medical condition which, in the opinion of the investigator, makes the patient unsuitable for inclusion.
- 10. Enrollment in another concurrent clinical interventional study, or intake of an investigational drug within three months or 5 half-lives prior to inclusion in this study, if considered interfering with this study objectives as assessed by the Investigator.
- 11. Foreseeable inability to cooperate with given instructions or study procedures.
- 12. Clinical suspicion of active mycobacteria histoplasma capsulatum, herpes zoster, salmonella and shigella Infections.
- 13. Patients with liver dysfunction defined as AST or $ALT > 5 \times ULN$

5.3.3 Withdrawal of patients from treatment or study

5.3.3.1 Withdrawal from treatment

A patient should be withdrawn from the study treatment if, in the opinion of the Investigator, it is medically necessary, or if it is the wish of the patient.

When a patient is withdrawn, the date of last IMP administration and the date and reason for treatment withdrawal should be clearly described in the relevant sections of the CRF. If a patient is removed from treatment because of an AE, the reason for treatment withdrawal should always be stated as 'adverse event' irrespective of whether this was the investigator's or the patient's decision.

The patient will continue to participate in the study without taking study treatment.

5.3.3.2 Withdrawal from study

Whenever possible and irrespective of the reason for withdrawal, the patient should be examined as soon as possible. Relevant samples should be obtained and all relevant assessments should be completed, preferably according to the schedule for Visit 6 (Day 15). The CRF should be completed as far as possible. Date and reason for the study withdrawal should be clearly described in the CRF.

5.3.4 Replacement of withdrawn patients

Patients withdrawn from the study will not be replaced.

5.3.5 Screening failures

Screening failures are defined as patients who consent to participate in the study but are not subsequently randomized into the study. A minimal set of screening failure information is required which includes demographics, reason for screen failure and failed eligibility criteria.

Patients who do not meet the criteria for participation in this study (screening failure) may not be rescreened.

5.4 Treatments

5.4.1 Treatments administered

The patients will receive investigational medicinal products (IMP) according to the randomization schedule, see Table 1.

Arm	Investigational product	Dosage form	Route	Daily dose	Dosage regimen		
А	Emapalumab	Solution	i.v. infusion	Day 1: 6 mg/kg Days 4, 7, 10, 13: 3 mg/kg	Every 3 rd day for in total 5 infusions		
В	Anakinra	Solution	i.v. infusion	Days 1-15: 400 mg/day in total, divided into 4 doses given every 6 hours	4 times daily for 15 days		
С	None	N/A	N/A	N/A	N/A		

Table 1

Investigational medicinal products

5.4.2 Identity of investigational medicinal products

Emapalumab and anakinra will be supplied to the study sites as open-label supplies.

Version 7.0 Final Protocol, Date 24 Jun 2020

Sobi	
Emapalumab/Anakinra	

Possible deficiencies related to the handling and quality of the IMPs should be reported to the study monitor and also directly to [contact].

5.4.2.1 Emapalumab

The IMP emapalumab is delivered as a sterile concentrate for infusion, prefilled in single-use glass vials which require a dilution prior to administration. The concentrate of emapalumab in the solution is 5 mg/mL. The solution contains no antimicrobial preservative, and therefore each vial must be used only once.

Emapalumab should be stored between 2 and 8°C (36 and 46°F) in a secure area at the study sites. Further instructions on handling and storage of emapalumab are available in the IMP manual.

Emapalumab is manufactured by a third-party manufacturing facility duly qualified by Sobi AG and is supplied as described in the IMP Manual.

Labeling will comply with national regulatory requirements.

5.4.2.2 Anakinra

The IMP anakinra is delivered as a sterile solution for injection, prefilled in a single-use syringe with the strength 100 mg. The total volume of injection is 0.67 mL and the concentration of anakinra in the solution is 150 mg/mL.

Anakinra must be stored at refrigerated conditions at 2-8 °C (36°-46°F) in a secure area at the study sites. Further instructions for handling and storage of the IMP anakinra are available in the IMP manual.

The anakinra drug substance is manufactured by Boehringer Ingelheim (Vienna, Austria) or by Pfizer (Strängnäs, Sweden) and anakinra drug product is manufactured by Patheon Italia SpA (Monza, Italy).

Labeling will comply with national regulatory requirements.

5.4.3 Method of assigning patients to treatment groups

The different treatment groups are;

Arm A: Emapalumab as add on to standard of care Arm B: Anakinra as add on to standard of care Arm C: Standard of care only

The ratio between the treatment groups is 1:1:1, i.e., the same number of patients will be randomized to emapalumab, anakinra, or standard of care. Patients will be stratified based on glucocorticoid treatment at randomization to ensure an equal distribution between treatment arms. The randomization numbers are generated in blocks. Each block includes the three treatment groups per the ratio described above. An IWRS will be used for the randomization.

Confidential

5.4.4 Selection of doses

5.4.4.1 Dose selection rationale for anakinra

Anakinra is approved for the chronic treatment of a number of inflammatory diseases as a subcutaneous treatment (at doses of 100 mg/day or in weight-based doses of up to 8 mg/kg/day). The i.v. administration of anakinra has been studied in clinical trials in healthy volunteers and in critically ill patients with sepsis and hyper-inflammation at variable i.v. doses up to 3500 mg/day over 72 hours: e.g., 2 mg/kg/hour, 20 mg/kg/day (<40 kg) and 916 mg/day (> 40kg), bolus of 100 mg followed by infusion of 2 mg/kg/hour. No safety concerns emerged in these studies [7, 8, 9, 10, and 11].

A study in children with systemic onset juvenile arthritis complicated by refractory macrophage activation syndrome is currently ongoing (NCT02780583) in which anakinra is administered at dose of 10 mg/kg/day to a maximum of dose of 200 mg/day divided every 12 hours (for children \leq 40 kg) or 5 mg/kg/day up to a maximum dose of 400 mg/day divided every 6 hours (children > 40 kg and adults). This dosing schema reflects the dose at which anakinra is administered, although off label, in children affected by this severe disease, as reported in a number of case studies.

Since the start of the current clinical study, there is emerging data based on anakinra given by i.v infusions in treament of cytokine storm syndromes (21), and emerging data of anakinra i.v administration studied in the SARS-CoV-2 setting (22).

Based on the above, in this study anakinra is administered at a total dose of 400 mg per day, divided in 4 i.v. doses of 100 mg every 6 hours.

5.4.4.2 Dose selection rationale for emapalumab

Preliminary data on inflammatory makers in blood, e.g., D-dimer, LDH and ferritin [4, and unpublished data generated in the laboratory of Immunology of the National Institute for Infectious Diseases and the Laboratory of ImmunoRheumatology of the Ospedale Pediatrico Bambino Gesù] indicate that patients with SARS-CoV-2 infection have longer and more marked inflammatory response. This seems to be more evident in patients with severe disease. These markers, though elevated, appear to be less elevated than what is generally observed in systemic onset Juvenile Idiopathic Arthritis (sJIA) patients who develop Macrophage Activation Syndrome (MAS), a form of secondary HLH. Furthermore, their evolution over time seem to be also less rapid. Of note, it must be mentioned that these observations in blood may not fully reflect the amount of IFN γ released in the inflamed lungs.

The emapalumab dosing scheme used in the ongoing NI-0501-06 study in sJIA/MAS patients (NCT03311854) foresees an initial dose of 6 mg/kg followed by 3 mg/kg every 3 days. The available data in the 9 patients who have completed treatment to date indicate the achievement of complete response in all the patients with no relevant safety or tolerability concern [12]. In the trial in primary HLH, doses up to 10 mg/Kg/infusion have been used again with no relevant safety or tolerability concern [16].

Confidential

Based on the above, an initial emapalumab dose of 6 mg/kg followed by 3 mg/kg every 3 days has been selected for the present study in SARS-CoV-2 infected patients.

This dose is considered appropriate to give the best chance to demonstrate efficacy in the specific patient population of this study, taking into account (I) the favourable safety profile of emapalumab not only in secondary, but also in primary HLH, (II) the life-threatening condition to be treated, (III) the low number of patients to be enrolled in the study (n=18), (IV) and the extremely challenging situation which the epidemic of SARS-CoV-2 infection represents.

5.4.4.3 Rationale for stratifying the use of glucocorticoids

As glucocorticoids are one of the main first line anti-inflammatory treatments in secondary HLH, they have been suggested as one of the potential treatments for patients with severe SARS-CoV-2 infection [14]. Further to the relevance of the hyper-production of inflammatory cytokines in this infection, initial promising data have been reported with the use of IL-6 targeted therapies, namely tocilizumab, in the treatment of patients with SARS-CoV-2 infection [15]. Noteworthy, in this report all patients treated with tocilizumab also received glucocorticoids.

The use of glucocorticoids in patients with SARS-CoV-2 differs between regions and countries. Based on the experience accumulated so far in Europe, glucocorticoids have become part of standard of care for SARS-CoV-2 patients with hyperinflammation. Meanwhile, in US glucocorticoids currently seem not to be widely used in the treatment of patients with SARS-CoV-2 and hyperinflammation.

Interim WHO guidance argues against the use of glucocorticoids in the treatment of patients with SARS-CoV-2 infection [19]. This view is supported by the Infectious Diseases Society of America Guidelines on the Treatment and Management of Patients with COVID-19 [20].

Glucocorticoids are anti-inflammatory and the potential use of glucocorticoids could have an impact on biomarkers of hyper-inflammation and potentially also on the clinical outcome.

Since the use of glucocorticoids will differ between regions study patients will be stratified based on glucocorticoid treatment at randomization to ensure an equal distribution between treatment arms.

5.4.5 Selection and timing of doses for each patient

5.4.5.1 Emapalumab

Emapalumab will be administered by intravenous (i.v.) infusion over a period of 1 to 2 hours depending on the volume to be infused, at an initial dose of 6 mg/kg.

Emapalumab treatment will be continued at the dose of 3 mg/kg, every 3rd day until Day 13 i.e., Days 4, 7, 10 and 13. The following information will be recorded in the CRF for each emapalumab administration: date, start and end time, total dose infused, and, if infusion was interrupted, reason for interruption.

Emapalumab must be prepared by a Pharmacist or other appropriately qualified staff member, specifically authorized by the Investigator/Pharmacist and appropriately licensed to perform the task.

The specific dose to be administered for an individual infusion will be determined based on the patient's body weight at screening.

Full instructions for the preparation of emapalumab, including dilution steps and method for administration, are available in the IMP manual.

The patient should receive the designated volume of the infusion material through an infusion pump over 1 to 2 hours depending on the volume to infuse. A 0.2 μ m filter must be included in all infusion lines.

It is recommended that an i.v. central line remains in place to ensure venous access during the treatment period.

Since no data are available on the compatibility of emapalumab with other i.v. substances or additives, other medications/substances should not be added to the infusion material or infused simultaneously through the same i.v. line. If the same i.v. line is used for subsequent infusions of other drugs, the line should be flushed appropriately with saline before and after infusion of emapalumab.

5.4.5.2 Anakinra

Anakinra will be administered by i.v. infusion at total dose of 400 mg per day, divided in 4 doses 100 mg i.v. every 6 hours.

Anakinra treatment will continue for 15 days i.e., Days 1 to 15. The following information will be recorded in the CRF for each anakinra administration: date, start and end time, total dose infused, and, if infusion was interrupted, reason for interruption.

Before administration, the full content of the prefilled, single-use syringe (anakinra 100 mg) will be diluted in 100 mL saline. The i.v. administration of anakinra has to occur immediately after the preparation over an infusion period of 60 minutes. A particle reduction inline filter will be assembled with the infusion set.

Full instructions for the preparation of anakinra are available in the IMP manual.

5.4.6 Blinding and unblinding

This is an open study with no level of blinding.

5.4.7 Concomitant therapy

5.4.7.1 Prophylactic therapy

For patients randomized to emapalumab, prophylaxis for Herpes Zoster virus infection has to be in place from the day before initiation of emapalumab treatment until end of study.

Version 7.0 Final Protocol, Date 24 Jun 2020

The prophylactic therapy will be recorded in the CRF.

5.4.7.2 Concomitant therapy

Concomitant use of IL-6 inhibitors (e.g., tocilizumab), non-anakinra IL-1 inhibitors (e.g, canakinumab), TNF inhibitors and JAK inhibitors is **not** allowed. If any of these therapies are initiated at the discretion of the Investigator e.g., as rescue therapy due to worsening of the patient's condition, then the patient should be withdrawn from study (see Section 5.3.3.2).

Hydroxychloroquine, chloroquine, glucocorticoid treatment, antimicrobial therapy and prophylaxis are not limited.

Analgesic treatment, transfusion of blood products, electrolyte and glucose infusions, i.v. parenteral nutrition, positive inotropic support, antibiotics, anti-fungal and anti-viral treatments (e.g, remdesivir), ultrafiltration or hemodialysis, as well as general supportive care are permitted.

Other therapy considered necessary for the patient's welfare may be given at the discretion of the Investigator.

For patients taking other treatments that are substrates for CYP450 with a narrow therapeutic index (e.g. warfarin and phenytoin), the treating physician should make appropriate treatment adjustments and monitor the patient as deemed necessary.

All relevant concomitant therapy, as defined by the Investigator, will be recorded in the CRF.

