	In patients showing worsening of clinical condition, independently of the treatment arm, the Investigator is completely free to decide to introduce any drug considered necessary for a given patient as rescue treatment.
Number of subjects planned:	The study will enroll a total of 54 patients, 18 per arm according to the 1:1:1 randomization.
Diagnosis and main criteria for inclusion:	Patients with documented SARS-CoV-2 infection, age > 18 to < 85 years with respiratory distress and hyperinflammation.

Assessments:

The clinical and laboratory parameters to be collected at given time points are indicated in the simplified Schedule of Events presented in the end of the synopsis. This schedule also includes information on the patient's demographics, medical history and prior medication.

Test product; dose and mode and duration of administration:

The patients will receive investigational medicinal products (IMP) according to the randomization schedule and table below.

Arm	IMP	Route	Daily dose	Dosage regimen
A	Ema- palumab	i.v. infusion	Day 1: 6 mg/kg Days 4, 7, 10, 13: 3 mg/kg	Every 3 rd day for in total 5 infusions
В	Ana- kinra	i.v. infusion	Days 1-15: 400 mg/day in total, divided into 4 doses given every 6 hours	4 times daily for 15 days
С	None	N/A	N/A	N/A

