Prophylactic Therapy: For patients randomized to emapalumab, prophylaxis for Herpes Zoster virus infection has to be in place from the day before initiation of emapalumab treatment until end of study Concomitant Therapy: Concomitant use of IL-6 inhibitors (e.g., tocilizumab), non-anakinra IL-1 inhibitors (e.g, canakinumab), TNF inhibitors and JAK inhibitors is not allowed. If any of these therapies are initiated at the discretion of the Investigator e.g., as rescue therapy due to worsening of the patient's condition, then the patient should be withdrawn from study. Hydroxychloroquine, chloroquine, glucocorticoid treatment, antimicrobial therapy and prophylaxis are not limited. Analgesic treatment, transfusion of blood products, electrolyte and glucose infusions, i.v. parenteral nutrition, positive inotropic support, antibiotics, antifungal and anti-viral treatments (e.g., remdesivir), ultrafiltration or hemodialysis, as well as general supportive care are permitted. The study will enroll a total of 54 patients, 18 per arm according to the 1:1:1 Determination of sample randomization. Patients will be stratified based on glucocorticoid treatment at size: randomization to ensure an equal distribution between treatment arms. The sample size has been estimated based on the following assumptions: An overall one-sided significance level for efficacy of 0.097 (9.7%) 1. and a power of 74% for each comparison under the assumption that the true success rates are 50% in the SoC group increasing to 80% in the emapalumab or anakinra groups. 2. The study will consist of two stages, with equal numbers of patients randomised into Stage 1 and into Stage 2 per treatment arm. 3. There is the potential to stop for futility of emapalumab or anakinra (or both) at the end of Stage 1. 4. The futility rule for stopping at the end of Stage 1 is binding.

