3.3 Potential risks and benefits

Anakinra is a recombinant form of the human IL-Ra, r-metHuIL-1Ra, which is produced by recombinant DNA technology in an E. coli expression system. Therapeutically, anakinra neutralizes the biological activity of IL-1 (IL-1 α and IL-1 β) by competitively inhibiting its binding to the IL-1RI.

Kineret (anakinra) was first approved for treatment of RA in the US in 2001 and subsequently in the EU/EEA in 2002. More than 3000 patients were included in this development program.

In 2012, an sBLA on anakinra for treatment of NOMID was approved in the US. Kineret is also approved for treatment of CAPS (in EU/EEA, Israel and Australia), Still's disease, including SJIA and AOSD (in EU/EEA), FMF (in EU/EEA), and SJIA (in Australia).

The initial IND for anakinra was granted in 1991. The estimated cumulative exposure to anakinra in completed company sponsored clinical studies up to 1 May 2018 is 6404 subject-years in 8518 subjects with various indications.

Anakinra is administered s.c. at doses of 100 mg/day (RA) or in weight-based doses of up to 8 mg/kg/day (NOMID). In clinical studies in sepsis, doses up to 2 mg/kg/hour i.v. over 72 hours were administered to >500 patients and were well tolerated. For additional information of i.v. administration of anakinra, see Section 5.4.4.1.

Based on the most recent PSUR (with data from May 1994 through to May 2019) the estimated exposure to anakinra in completed company sponsored clinical studies is 6404 subject-years in 8518 subjects. The cumulative post-marketing exposure is estimated to 113 414 patient years.

The safety profile of anakinra has been consistent across indications, age groups, and doses studied; this includes data that have been reported in the literature for off-label indications. The safety profile has remained stable also when anakinra has been studied in long-term safety studies and in patients with various co-morbidities. There are no indications of increasing AE rates over time. The most common AEs are non-serious, mostly mild to moderate injection site reaction that usually occur early and resolve during continued anakinra treatment. No dose-limiting toxicities have been observed in clinical studies or during post-marketing use and the maximum tolerated dose has not been established. There are no indications of changes to the safety profile even when very high doses are administered.

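### The anakinra exemption in the prohibited-drug list is not limited to Arm B, so a control may receive commercial anakinra as rescue within the rules, at a modest cost in power

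*Protocol*

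**What the plan says.** Protocol 5.4.7.2 states that "Concomitant use of IL-6 inhibitors (e.g., tocilizumab), non-anakinra IL-1 inhibitors (e.g, canakinumab), TNF inhibitors and JAK inhibitors is" not allowed. The synopsis has the same list ("non-anakinra IL-1 inhibitors (e.g, canakinumab), TNF inhibitors and JAK inhibitors is not allowed"). Neither text ties the anakinra exemption to an arm, and neither names emapalumab or any other interferon-gamma blocker.

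If a listed drug is started, for example as rescue, "then the patient should be withdrawn from study". That consequence attaches to the listed classes only. Section 5.4.7.2 goes on to say that other therapy needed for the patient's "welfare may be given at the discretion of the Investigator". Section 5.1 and the synopsis go further: when a patient worsens, in any arm, "the Investigator is completely free to decide to introduce any drug considered necessary for a given patient as rescue treatment".

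Section 5.4.3 labels the control group "Arm C: Standard of care only". Section 5.4.8 covers accountability for study supplies. On recording, 5.4.7.2 says "All relevant concomitant therapy, as defined by the Investigator, will be recorded in the CRF"; SAP 11 tabulates medication started after randomization.

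Efficacy is analysed by randomized group (Protocol 7.2, SAP 7.1). Protocol 7.3.8 and SAP 8.2.1 and 8.5.1 score a patient who discontinues before Day 15 and was never on IMV or ECMO as a success. A death by Day 15 is a failure.

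**The concern.** The exemption has an obvious purpose: Arm B receives anakinra. As worded, it also covers Arms A and C. With the open rescue sentences, an investigator with a worsening control patient can give commercial anakinra and commit no deviation. The Arm C label describes an allocation and does not restrict rescue. Drug accountability concerns study supplies and does not reach marketed product.

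The anakinra route is plausible. Section 3.3 says "Kineret (anakinra) was first approved for treatment of RA in the US in 2001 and subsequently in the EU/EEA in 2002", Section 5.4.4.1 points to emerging intravenous data in this disease, and the study is open label. Tocilizumab, the alternative that the protocol itself discusses (5.4.4.3), leads to withdrawal; anakinra does not. For emapalumab, the documents show only FDA approval for primary HLH and 70 patients treated in the US since then, so that route is remote and confined to US sites.

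The trial asks whether adding each drug to standard of care avoids ventilation. If a drug works and some controls receive it before ventilation or death, the control success rate rises and the contrast shrinks. With 18 per arm and planned power of 74%, there is little margin. The chance of a binding futility stop also rises.

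**Working it through.** **Inputs from the documents** (Protocol 7.1 and 7.3.6; SAP 5.1): success 50% on standard of care and 80% on active; 18 per arm, interim at 9 per arm; one-sided Fisher's exact test; efficacy if p < 0.025 at Stage 1 or p < 0.159 at Stage 2; binding futility if p > 0.690.

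**Assumptions** (not in the documents): *c*, the share of controls given off-allocation study drug; and *b*, the fraction of the 30-point benefit they receive. The main case is *b* = 0.5, because rescue follows worsening. Full benefit (*b* = 1) is a worst case.

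**Method.** Exact enumeration of all 100 Stage 1 outcomes. Each is classed as a futility stop, efficacy, or continuation, and continuations are carried through all Stage 2 outcomes:

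power = P(efficacy at Stage 1) + Σ P(Stage 1 outcome continues) × P(Stage 2 p < 0.159 given that outcome).

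**Plan's own figure.** With no crossover, power is 73.6%, which reproduces the stated 74%. The futility stop is 10.6%.

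**Dilution.** Control success = 0.50 + 0.30 × *c* × *b*.

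| Controls rescued (*c*) | Control rate, *b* = 0.5 | Power | Futility stop | Power, *b* = 1 |
|---|---|---|---|---|
| 0 | 0.500 | 73.6% | 10.6% | 73.6% |
| 1 of 18 | 0.508 | 71.8% | 11.4% | 70.0% |
| 10% | 0.515 | 70.3% | 12.0% | 66.9% |
| 2 of 18 | 0.517 | 70.0% | 12.2% | 66.2% |
| 20% | 0.530 | 66.9% | 13.6% | 59.7% |
| 30% | 0.545 | 63.4% | 15.2% | 52.0% |

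**Sensitivity to the futility region.** The outcomes listed in SAP Table 1, with those more extreme, cover 35 of 100 outcomes; p > 0.690 covers 53. Under the Table 1 region, power at half benefit goes from 76.1% to 73.0% (*c* = 10%) and 69.6% (20%). The futility stop goes only from 1.5% to 1.8% and 2.1%.

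**Same share in both arms.** The assumed effect cuts failures from 50% to 20%, a 60% reduction; half of that is 30%. If a share *c* of each arm gets the other drug at half benefit, both failure rates are multiplied by (1 − 0.3*c*). At 10% the rates are 0.515 and 0.806 and power is 71.7%; at 20% they are 0.530 and 0.812 and power is 69.8%.

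**What a bare prohibition could do.** Suppose anakinra is barred and every control who would have received it gets tocilizumab before any ventilation, is withdrawn, and is scored a success. Taking their success rate otherwise as 50%, control success = 0.50 + 0.50 × *c*.

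| *c* | Power as written (half benefit) | Power if all switch and score as success |
|---|---|---|
| 1 of 18 | 71.8% | 67.5% |
| 10% | 70.3% | 62.2% |
| 20% | 66.9% | 49.4% |

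If only a fraction *s* switch and the rest gain nothing from other rescue, the bar breaks even where 0.50 × *s* = 0.15, that is *s* = 30%. Above that it lowers power.

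**The case against.** Free rescue with analysis as randomized is a coherent choice for an open-label proof-of-concept trial set up in an emergency, and narrowing rescue has an ethical cost. Nothing in the plan invites study drug in Arm C; the treatment table gives that arm no product, and many investigators would read such use as off-protocol. Every crossover rate above is assumed. One rescued control costs 1.8 points, less than the 2.5 points that separate the two futility regions. Concomitant medication is collected at Visits 1 to 7, and an immunomodulator given as rescue would hardly be judged irrelevant. A control given anakinra today already stays in follow-up with the observed outcome. A bar that leaves the withdrawal scoring untouched could do harm.

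Most of this stands. It limits the size of the problem and shapes the remedy. It does not remove the gap: the plan already bars drugs of similar action, so leaving anakinra open in Arms A and C looks like an omission more than a decision about rescue. Confining the exemption to Arm B fits the plan's own logic.

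**Conclusion.** The gap is real and the loss is probably modest. The wording allows commercial anakinra as rescue in a standard-of-care or emapalumab patient, who is then analysed as randomized. With one or two of 18 controls rescued at half benefit, power falls from 73.6% to about 70–72%; at 20% it is 66.9%. These figures assume that the drug works, that it is given before ventilation or death, and that rescued controls would otherwise have the 50% success rate. Use in controls biases towards no difference and creates no false positive.

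A reader might infer three stronger things that the documents do not support:

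- That power drops to 52–60%. This needs 20–30% of controls rescued with full benefit, and no document gives a rescue rate.
- That the emapalumab route matters as much as the anakinra route. The documents show it as marketed only in the US, with few patients treated.
- That adding both drugs to the barred list is enough. Under the present withdrawal and scoring rules, this could lower power further.

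Priority: minor to moderate.

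**What to change.** 1. In 5.4.7.2 and the synopsis, limit the anakinra exemption to allocated study drug in Arm B, and bar off-allocation anakinra and emapalumab in all arms through Day 15. Cross-refer to this at the rescue sentence in 5.1.
2. For any barred rescue drug (these two and the four classes already listed), stop study treatment if needed, keep the patient in follow-up, and use the observed Day 15 IMV, ECMO and death status in the as-randomized analysis. This replaces withdrawal from study in 5.4.7.2 and, for these patients, the scoring of never-ventilated discontinuations as successes in Protocol 7.3.8 and SAP 8.2.1 and 8.5.1.
3. Record all such use with its start date in the CRF, in every arm, whether or not the investigator considers it relevant.

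The cost is a few sentences across 5.4.7.2, 5.1, the synopsis, 7.3.8 and the two SAP sections, plus one CRF item; no analysis is added. Investigators lose one unrestricted rescue option. The bar reduces dilution only as far as it is followed, since a patient rescued against it still counts in the assigned arm. Use after Day 15 stays open, so overall survival and time to discharge are not protected.
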